## 9.6 DATA MANAGEMENT

For the CNSR, all hospitals participating in the CNSR were selected by a Steering Committee using a convenient sampling method from the China National Network of Stroke Research developed by the National Center of Quality Management in Stroke Care. In total, 491 hospitals were included based on their geographic region, teaching status, hospital beds, and annual stroke discharges. The internal data validity of CNSR I, II, and III were ensured by introducing trained clinical research coordinators (CRCs) to these studies to guarantee the quality of data entry. The CRCs examined all medical records of stroke or TIA patients to identify eligible cases for the registries. The operating books were printed and sent to each

researcher and coordinator for guidance. Independent contract research organizations (CROs) were invited to monitor the study procedures and to ensure the quality of data entry. All data elements collected by PRF, web-based CRF, or EDC system were manually or mechanically checked for completeness, coding correctness, and appropriateness of the diagnostic algorithm conducted by a research specialist from independent CROs throughout the study period. A professional data processing company was responsible for the computer or PAD data entry. The Data Management Group of the National Clinical Research Center for Neurological Diseases (NCRC-ND) served as the data analysis department and analyzed the aggregated de-identified data for research purposes.

For the current study, the data will be managed by NCRC-ND. Data management, tabulations, and graphics will be carried out with SAS version 9.3 software (SAS institute). Source code of data management and data analyses will be kept for inspection for at least five years after publication of the results.

## **9.7 DATA ANALYSIS**

### **9.7.1 Main analysis**

[figure not shown]
For continuous data, descriptive statistics (number of patients, mean, standard deviation (SD), minimum, median, interquartile range, and maximum) will be presented. Categorical data will be presented as frequency and proportion with 95% CI. Unless otherwise stated, the calculation will be based on the available data. No data imputation will be performed for the missing data. Details for all analyses will be provided in the statistical analysis plan (SAP).

[REDACTED]

[REDACTED]

[REDACTED]

[REDACTED]

## **9.8     QUALITY CONTROL**

For the CNSR, safety and risk control was assessed by the Data Safety and Monitoring Board (DSMB) before the study. Clinical research associates conducted data verification on site during the study. Data management team of NCRC-ND performed remote real time data supervision for all the data cleaning, integration, analysis, and other processing.

For the current study, the standard operation procedures (SOPs) of Boehringer Ingelheim (BI), such as NISed SOP, will be strictly followed. In addition, key elements of the International Society for Pharmacoepidemiology Good Pharmacoepidemiology Practices (GPP) will be followed [\[R16-5416\]](#). The statistical analysis method will be reviewed and repeated by a second analyst. All the data cleaning, integration, analysis, and other processing will be conducted

under the guidance and supervision of data management team of NCRC-ND. The study report will be reviewed, approved, and archived per SOPs of BI.

## **9.9 LIMITATIONS OF THE RESEARCH METHODS**

The quality of a study based on existing data relies on accuracy of recorded data. Important data may not be available. The hospitals participating in the CNSR, although spread throughout China and covered all geographic areas, were mainly selected by convenience in nature. These hospitals possess more resources and expertise in ischemic stroke when compared to other hospitals in China, especially those at a country-level or lower ranks. Therefore, results from the current study will have to be interpreted with caution as it is not known what proportion of stroke patients in China have access to hospital cares at a level similar to those participated in the CNSR. Due to the nature of explore existing data, the interpretation is based on non-missing data.

## **9.10 OTHER ASPECTS**

CNSR I, II, and III data collection were initiated after receiving approval from the central institutional review board at [REDACTED]. The informed consent forms (ICFs) were provided by patients or their legal representatives.

For the current study, the study protocol will be submitted to [REDACTED] Institutional Review Board (IRB)/Independent Ethics Committee (IEC) for review. The IRB/IEC approval will be obtained before the study initiation. A waiver for the ICF will be applied since the study will use existing data.

## **9.11 SUBJECTS**

### **9.11.1 Cases**

Not applicable.

### **9.11.2 Controls**

Not applicable.

## **9.12 BIAS**

Refer to Section [9.9](#).

## **10. PROTECTION OF HUMAN SUBJECTS**

The section is not applicable since the current study is a time-trend analysis of the data collected from the CNSR I to III.

The procedures set out in this study protocol are designed to ensure that the sponsor and investigator abide by the principles of the GPP guidelines [\[R16-5416\]](#). The study also will be carried out in keeping with local legal requirements.

## **11. MANAGEMENT AND REPORTING OF ADVERSE EVENTS/ADVERSE REACTIONS**

The current study is a time-trend analysis of the existing data collected from the CNSR I to III. Boehringer Ingelheim or third party acting on behalf of BI will not have access to individual patient data during the study. Data will be provided to BI in aggregated manner. Thus, collection and reporting of adverse events (AEs)/adverse drug reactions (ADRs) is not applicable.

## **12. PLANS FOR DISSEMINATING AND COMMUNICATING STUDY RESULTS**

The final report of the study report is planned in March 2020. Results of this non-interventional study will be disclosed on encepp.eu and clinicaltrials.gov.

A conference abstract and at least one manuscript will be generated from the study.

## **ANNEX 1. LIST OF STAND-ALONE DOCUMENTS**

None

## **ANNEX 2. ENCEPP CHECKLIST FOR STUDY PROTOCOLS**

**Study title:** Temporal trends of thrombolysis treatment in Chinese acute ischemic stroke (AIS) patients from 2007-2017: analysis of China National Stroke Registry (CNSR) I, II, and III

**EU PAS Register® number:** Not applicable

**Study reference number (if applicable):**

Section 1: Milestones	Yes	No	N/A	Section Number
1.1 Does the protocol specify timelines for				
1.1.1 Start of data collection 				
1.1.2 End of data collection 				
1.1.3 Progress report(s)				
1.1.4 Interim report(s)				
1.1.5 Registration in the EU PAS Register®				
1.1.6 Final report of study results.				

Comments:

Section 2: Research question	Yes	No	N/A	Section Number
2.1 Does the formulation of the research question and objectives clearly explain:				
2.1.1 Why the study is conducted? (e.g. to address an important public health concern, a risk identified in the risk management plan, an emerging safety issue)				
2.1.2 The objective(s) of the study?				
2.1.3 The target population? (i.e. population or subgroup to whom the study results are intended to be generalised)				
2.1.4 Which hypothesis(-es) is (are) to be tested?				
2.1.5 If applicable, that there is no a priori hypothesis?				

Comments:

Section 3: Study design	Yes	No	N/A	Section Number
3.1 Is the study design described? (e.g. cohort, case-control, cross-sectional, other design)				

 Date from which information on the first study is first recorded in the study dataset or, in the case of secondary use of data, the date from which data extraction starts.

 Date from which the analytical dataset is completely available.

Section 3: Study design	Yes	No	N/A	Section Number
3.2 Does the protocol specify whether the study is based on primary, secondary or combined data collection?				
3.3 Does the protocol specify measures of occurrence? (e.g., rate, risk, prevalence)				
3.4 Does the protocol specify measure(s) of association? (e.g. risk, odds ratio, excess risk, rate ratio, hazard ratio, risk/rate difference, number needed to harm (NNH))				
3.5 Does the protocol describe the approach for the collection and reporting of adverse events/adverse reactions? (e.g. adverse events that will not be collected in case of primary data collection)				

Comments:

--

Section 4: Source and study populations	Yes	No	N/A	Section Number
4.1 Is the source population described?				
4.2 Is the planned study population defined in terms of:				
4.2.1 Study time period				
4.2.2 Age and sex				
4.2.3 Country of origin				
4.2.4 Disease/indication				
4.2.5 Duration of follow-up				
4.3 Does the protocol define how the study population will be sampled from the source population? (e.g. event or inclusion/exclusion criteria)				

Comments:

--

Section 5: Exposure definition and measurement	Yes	No	N/A	Section Number
5.1 Does the protocol describe how the study exposure is defined and measured? (e.g. operational details for defining and categorising exposure, measurement of dose and duration of drug exposure)				
5.2 Does the protocol address the validity of the exposure measurement? (e.g. precision, accuracy, use of validation sub-study)				
5.3 Is exposure categorised according to time windows?				
5.4 Is intensity of exposure addressed? (e.g. dose, duration)				
5.5 Is exposure categorised based on biological mechanism of action and taking into account the pharmacokinetics and pharmacodynamics of the drug?				
5.6 Is (are) (an) appropriate comparator(s) identified?				

Comments:

--

Section 6: Outcome definition and measurement	Yes	No	N/A	Section Number
6.1 Does the protocol specify the primary and secondary (if applicable) outcome(s) to be investigated?				
6.2 Does the protocol describe how the outcomes are defined and measured?				
6.3 Does the protocol address the validity of outcome measurement? (e.g. precision, accuracy, sensitivity, specificity, positive predictive value, use of validation sub-study)				
6.4 Does the protocol describe specific outcomes relevant for Health Technology Assessment? (e.g. HRQoL, QALYs, DALYs, health care services utilisation, burden of disease or treatment, compliance, disease management)				

Comments:

--

Section 7: Bias	Yes	No	N/A	Section Number
7.1 Does the protocol address ways to measure confounding? (e.g. confounding by indication)				
7.2 Does the protocol address selection bias? (e.g. healthy user/adherer bias)				
7.3 Does the protocol address information bias? (e.g. misclassification of exposure and outcomes, time-related bias)				

Comments:

--

Section 8: Effect measure modification	Yes	No	N/A	Section Number
8.1 Does the protocol address effect modifiers? (e.g. collection of data on known effect modifiers, subgroup analyses, anticipated direction of effect)				

Comments:

--

Section 9: Data sources	Yes	No	N/A	Section Number

Section 9: Data sources	Yes	No	N/A	Section Number
9.1 Does the protocol describe the data source(s) used in the study for the ascertainment of:				
9.1.1 Exposure? (e.g. pharmacy dispensing, general practice prescribing, claims data, self-report, face-to-face interview)				
9.1.2 Outcomes? (e.g. clinical records, laboratory markers or values, claims data, self-report, patient interview including scales and questionnaires, vital statistics)				
9.1.3 Covariates and other characteristics?				
9.2 Does the protocol describe the information available from the data source(s) on:				
9.2.1 Exposure? (e.g. date of dispensing, drug quantity, dose, number of days of supply prescription, daily dosage, prescriber)				
9.2.2 Outcomes? (e.g. date of occurrence, multiple event, severity measures related to event)				
9.2.3 Covariates and other characteristics? (e.g. age, sex, clinical and drug use history, co-morbidity, co-medications, lifestyle)				
9.3 Is a coding system described for:				
9.3.1 Exposure? (e.g. WHO Drug Dictionary, Anatomical Therapeutic Chemical (ATC) Classification System)				
9.3.2 Outcomes? (e.g. International Classification of Diseases (ICD), Medical Dictionary for Regulatory Activities (MedDRA))				
9.3.3 Covariates and other characteristics?				
9.4 Is a linkage method between data sources described? (e.g. based on a unique identifier or other)				

Comments:

--

Section 10: Analysis plan	Yes	No	N/A	Section Number
10.1 Are the statistical methods and the reason for their choice described?				
10.2 Is study size and/or statistical precision estimated?				
10.3 Are descriptive analyses included?				
10.4 Are stratified analyses included?				
10.5 Does the plan describe methods for analytic control of confounding?				
10.6 Does the plan describe methods for analytic control of outcome misclassification?				
10.7 Does the plan describe methods for handling missing data?				
10.8 Are relevant sensitivity analyses described?				

Comments:

--

Section 11: Data management and quality control	Yes	No	N/A	Section Number
11.1 Does the protocol provide information on data storage? (e.g. software and IT environment, database maintenance and anti-fraud protection, archiving)				
11.2 Are methods of quality assurance described?				
11.3 Is there a system in place for independent review of study results?				

Comments:

--

Section 12: Limitations	Yes	No	N/A	Section Number
12.1 Does the protocol discuss the impact on the study results of: 12.1.1 Selection bias? 12.1.2 Information bias? 12.1.3 Residual/unmeasured confounding? (e.g. anticipated direction and magnitude of such biases, validation sub-study, use of validation and external data, analytical methods).	  	  	  	
12.2 Does the protocol discuss study feasibility? (e.g. study size, anticipated exposure uptake, duration of follow-up in a cohort study, patient recruitment, precision of the estimates)				

Comments:

--

Section 13: Ethical/data protection issues	Yes	No	N/A	Section Number
13.1 Have requirements of Ethics Committee/ Institutional Review Board been described?				
13.2 Has any outcome of an ethical review procedure been addressed?				
13.3 Have data protection requirements been described?				

Comments:

--

Section 14: Amendments and deviations	Yes	No	N/A	Section Number

Section 14: Amendments and deviations	Yes	No	N/A	Section Number
14.1 Does the protocol include a section to document amendments and deviations?				

Comments:

Section 15: Plans for communication of study results	Yes	No	N/A	Section Number
15.1 Are plans described for communicating study results (e.g. to regulatory authorities)?				
15.2 Are plans described for disseminating study results externally, including publication?				

Comments:

Name of the main author of the protocol: \_\_\_\_\_

Date: dd/Month/year

Signature: \_\_\_\_\_

## ANNEX 3. ADDITIONAL INFORMATION

### A3-1 DIVISION OF EASTERN, CENTRAL, AND WESTERN CHINA [R20-1011]

The eastern region includes 11 provinces and municipalities in Beijing, Tianjin, Hebei, Liaoning, Shanghai, Jiangsu, Zhejiang, Fujian, Shandong, Guangdong, and Hainan; the central region includes 8 provinces in Shanxi, Jilin, Heilongjiang, Anhui, Jiangxi, Henan, Hubei, and Hunan; the western region includes 12 provinces, autonomous regions, and municipalities in inner Mongolia, Chongqing, Guangxi, Sichuan, Guizhou, Yunnan, Tibet, Shaanxi, Gansu, Qinghai, Ningxia, and Xinjiang.

### A3-2 DOCUMENTED INTRAVENOUS THROMBOLYTICS ABSOLUTE CONTRAINDICATIONS

For CNSR I:

- Aged above 80 years;
- CT evidence of intracranial haemorrhage;
- CT evidence of early signs of large cerebral infarction;
- Concurrence of epileptic seizures during ischemic;
- Have suffered a stroke or severe head injury in the past 3 months;
- Uncontrolled hypertension despite active treatment. Uncontrolled hypertension refers to systolic blood pressure > 185 mmHg or diastolic blood pressure > 110 mmHg, measured at least 10 minutes apart and repeated 3 times;
- Known hemorrhagic condition with significant bleeding disorder at onset or within the past 6 months;
- Acute pancreatitis or proven ulcerative gastrointestinal disease within 3 months;
- Recent invasive cardiopulmonary resuscitation or childbirth within 10 days. Non-stress vascular puncture (such as subclavian vein or femoral vein puncture);
- Blood glucose < 50 mg/dl (2.7 mmol/l) or > 400 mg/dl (22.2 mmol/l);
- Platelet count < 10^5/mm^3;
- Prothrombin time (PT) (international normalized ratio [INR]) > 1.5 or PT > 15 or activated partial thromboplastin time (APTT) > 40 sec.

For CNSRII and III:

- Uncontrolled hypertension despite active treatment. Uncontrolled hypertension refers to systolic blood pressure > 185 mmHg or diastolic blood pressure > 110 mmHg (;
- Concurrence of epileptic seizures during ischemic stroke;
- Recent surgery or trauma within 15 days;
- Recent intracranial or spinal surgery, head trauma, or stroke within 3 months;
- Previous history of intracranial haemorrhage, aneurysm, vascular malformation, or brain tumor;
- Active visceral bleeding within 22 days;

- Platelet count  $<10^5/\text{mm}^3$ , APTT (after heparin treatment)  $> 40 \text{ sec}$ , PT  $> 15$  or PT (INR)  $> 1.7$ , or known hemorrhagic condition/suspected subarachnoid hemorrhage
- CT evidence of ICH, SAH, or signs of large infarction.

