**2) IVT-eligible patients (patient groups B and B')**

1. Inclusion criteria:

- (1) Met the in- and exclusion criteria of "all AIS patients"
- (2) Arrived at hospital within 2h (patient group B) or 3.5h (patient group B') of symptom onset

2. Exclusion criteria:

- (1) Missing key data including
  - i. symptom onset time (or last known well time);
  - ii. hospital arrival time;
  - iii. whether received IVT treatment or not;
  - iv. the time of IVT treatment
- (2) Documented IVT absolute contraindications, according to the case report form (CRF) for each wave of CNSR (please refer to [ANNEX 3](#) for details)

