### 9.3.2 Outcomes

#### 9.3.2.1 Primary outcomes

For all the three waves of CNSR, the following primary outcomes will be assessed:

- Proportion of patients who received IV-rtPA treatment within 3h of symptom onset (patient group C, please refer to [Figure 1](#) for details on patient groups) among 2h IVT-eligible patients (patient group B);
- Proportion of patients who received IV-rtPA treatment within 4.5h of symptom onset (patient group C') among 3.5h IVT-eligible patients (patient group B').

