- Platelet count <105/mm³, APTT (after heparin treatment) > 40 sec, PT > 15 or PT (INR) > 1.7, or known haemorrhagic condition/suspected subarachnoid haemorrhage;
- CT evidence of ICH, SAH, or signs of large infarction.

IV-rtPA-treated patients (patient groups C and C')Inclusion criteria:

1. Met the in- and exclusion criteria of “IVT-eligible patients”
2. Treated with IV-rtPA within 3h (patient group C) or 4.5h (patient group C') of symptom onset

Exclusion criteria:

1. Not received IVT
2. Received IVT other than rtPA
3. Treated with IV-rtPA after 3h (group C) or 4.5h (group C') of symptom onset
4. Received additional treatments with intra-arterial reperfusion or experimental therapies

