8.2 OUTCOMES

8.2.1 Primary outcomes

For all the three waves of CNSR, the following primary outcomes will be assessed:

- Proportion of patients who received IV-rtPA treatment within 3h of symptom onset (patient group C) among 2h IVT-eligible patients (patient group B);
- Proportion of patients who received IV-rtPA treatment within 4.5h of symptom onset (patient group C') among 3.5h IVT-eligible patients (patient group B').

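### The IVT-eligible denominators B and B' rest on a different contraindication list in CNSR I than in CNSR II and III, so part of a change from CNSR I to a later wave can be a change of definition

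*Protocol*

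**What the plan says.** The primary outcomes are C/B (rtPA within 3h among eligible patients arriving within 2h) and C'/B' (within 4.5h among those arriving within 3.5h), for each wave (Protocol 9.3.2.1; SAP 8.2.1). SAP Table 1 sets the three waves side by side, and the primary objective is temporal change.

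Eligibility excludes "Documented IVT absolute contraindications, according to the case report form (CRF) for each wave of CNSR" (Protocol 9.2). Protocol Annex 3, A3-2 and SAP 7.2 then give one list for CNSR I and another for CNSR II and III:

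- **CNSR I only:** blood glucose limits; pancreatitis or gastrointestinal ulcer; recent resuscitation, childbirth or vascular puncture; a blood pressure condition "measured at least 10 minutes apart and repeated 3 times"; and "Prothrombin time (PT) (international normalized ratio [INR]) > 1.5 or PT > 15".
- **CNSR II and III only:** surgery or trauma within 15 days; intracranial or spinal surgery within 3 months; earlier intracranial haemorrhage, aneurysm, malformation or tumour; active visceral bleeding within 22 days; suspected subarachnoid haemorrhage; a heparin condition on APTT; and "PT > 15 or PT (INR) > 1.7".
- **Common to both:** the 185/110 mmHg limits, seizure, recent stroke or head injury, platelet count, PT above 15, APTT above 40 seconds, and CT haemorrhage or large infarction.

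The limitations section (Protocol 9.9) covers data accuracy, convenience sampling of hospitals and missing data. It does not mention the change of list, and the bias section (9.12) only refers back to it.

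**The concern.** The study asks how the treated proportion moved between waves. A proportion compared over time needs a denominator built by the same rule, or at least an account of how much the rule moved. Here the rule changes between CNSR I (2007-2008) and CNSR II (2012-2013). The 2010 guideline update, whose effect the study wants to understand, falls in the same gap, so a change of list and a change in practice would appear in the same comparison.

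That comparison is also the small one: Protocol 9.5 assumes 4% in CNSR I and 5% in CNSR II, and says the waves can be distinguished. A modest net difference in who is excluded could create, hide or exaggerate part of a one-point step, and a reader of Table 1 could not tell.

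**Working it through.** **Inputs from the documents.** Assumed proportions 4%, 5% and 28% with their intervals, and total AIS patients 14704, 19604 and 15204 (Protocol 9.5). SAP 7.2 gives 12415 for CNSR I. Not given: how many patients each list excludes, or how often those patients received rtPA. These are assumed below.

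**1. The plan's own intervals.** p ± 1.96·√(p(1−p)/N), with N the total AIS patients:

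- CNSR I: 0.04 ± 1.96·√(0.04·0.96/14704) gives 3.68-4.32% (3.66-4.34% with N = 12415)
- CNSR II: 0.05 ± 1.96·√(0.05·0.95/19604) gives 4.69-5.31%
- CNSR III: 0.28 ± 1.96·√(0.28·0.72/15204) gives 27.29-28.71%

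These round to the stated intervals. They use all AIS patients, not the smaller groups B or B'. If the eligible are 5% to 30% of AIS patients (assumed), the CNSR I interval is 2.6-5.4% to 3.4-4.6% and the CNSR II interval 3.6-6.4% to 4.4-5.6%. These overlap. That is a separate matter, but it shows that the I-to-II step has little room for a further source of error.

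**2. CNSR I under the later list, if that list is stricter on net.** Let r be the net extra share of the CNSR I denominator removed, and q the rtPA proportion among those removed. Then p' = (p − r·q)/(1 − r), with p = 4%.

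**3. CNSR I under the later list, if that list is looser on net.** Let s be the share of the enlarged denominator made up of added patients, all untreated. Then p' = p·(1 − s).

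| r or s (assumed) | Stricter, q = 0 | Stricter, q = 2% | Stricter, q = 4% | Looser, added patients untreated |
|---|---|---|---|---|
| 5% | 0.04/0.95 = 4.21% | 4.11% | 4.00% | 0.04·0.95 = 3.80% |
| 10% | 0.04/0.90 = 4.44% | 4.22% | 4.00% | 0.04·0.90 = 3.60% |
| 20% | 0.04/0.80 = 5.00% | 4.50% | 4.00% | 0.04·0.80 = 3.20% |

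**4. Set against the assumed steps.** With q = 0, the shifts of 0.21, 0.44 and 1.00 points are 21%, 44% and 100% of the one-point I-to-II step. They are 0.9%, 1.9% and 4.2% of the 24-point I-to-III step. Turning 4% into 28% by definition alone would need r = 1 − 4/28, about 86%. If the later list is looser, the effect reverses: CNSR I would stand at 3.2% to 3.8% on that list, and a reported 4%-to-5% step would understate the change.

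**5. Items that do nothing.** The CNSR I item for age above 80 has no effect, because group A is limited to 18-80 years in every wave. The INR limits are joined by an or to PT above 15 in both lists. The 1.5 versus 1.7 difference therefore matters only for patients with INR above 1.5 and up to 1.7, PT of 15 or less, and no other listed item.

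**6. Does the planned C/A outcome settle it?** C must meet the criteria for B, so the wave's own list can still remove treated patients from the numerator. If no treated patient has a documented contraindication (the q = 0 column), it removes nobody, and C/A is free of the list effect. Even then, C/A moves with the share of patients who arrive within 2h or 3.5h. It is a partial check.

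**The case against.** The strongest reply is that the wave-specific rule is stated openly, the forms are historical and cannot be changed, and the visible analysis is descriptive, with no formal comparison between waves. Many items are shared, and some that look unique overlap in part: CNSR I has bleeding-disorder and ulcer items that sit close to the later visceral bleeding item. Nothing in the documents supports a net difference as large as the 20% needed to produce the whole assumed I-to-II step.

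All of this stands, and it limits the point. It does not remove it: the lists are disclosed, but their effect on comparability is not discussed, and the descriptive comparison of waves is the purpose of the study.

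A reader might also infer that any rise across the three waves is suspect. The documents do not support that, because CNSR II and III share one list. Nor do they support the inference that the change of list inflates the later figures: each list has items the other lacks, so the net direction is open.

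Nor can one say that no harmonised analysis is planned. Text after Protocol 9.7.1 is redacted, the SAP numbering goes from 11.1 to 11.3 and the mock tables from 1 to 3.1, and most rows of the variable dictionary are blacked out.

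**Conclusion.** The point holds for comparisons of CNSR I with a later wave, and in practice for the small I-to-II step. Its direction and size cannot be derived from the documents. The working shows 4.0% moving to between 3.2% and 5.0% for assumed net shares up to 20%, with no shift at all if the affected patients were treated at the same rate as the rest. The assumed 28% in CNSR III is not threatened, and the II-to-III step is untouched.

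This is a disclosed design feature whose consequence is left unexamined, not a contradiction between passages, and nothing here bears on which list is clinically right. Measuring the effect is cheap and worth doing.

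**What to change.** Unless the redacted text already provides it, add to SAP Table 1 for each wave:

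1. A sensitivity row: rtPA within 3h among group A patients arriving within 2h, and within 4.5h among those arriving within 3.5h. Leave the contraindication exclusion out of both numerator and denominator. Keep all other group A, B and C rules as they are, including missing key times, rtPA only, and no intra-arterial or experimental therapy.
2. The number and percentage of early arrivals removed by the TPA_AC flag.

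Where item-level data exist, repeat C/B and C'/B' using only the items recorded the same way in all three waves.

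State in the SAP that a CNSR I-to-II change seen in C/B or C'/B' but not in row 1 will be reported as possibly definitional. Agreement with row 1 supports a practice change but does not prove one, because the hospitals (132 versus 219 in the protocol, chosen by convenience) and the data capture (paper versus web forms) also differ. Name the change of list in Protocol 9.9.

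The cost is a few table rows and one SAP paragraph, from existing data. The downside is that row 1 includes patients who could not properly be treated. Its level will be lower, and it is a comparability check, not a replacement for the primary proportions.
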